#### **Data management**

This proposed research follows the data management guidelines of War Child's Research & Development (R&D) department (available upon request). All electronic data files will be stored on a password protected cloud server (SharePoint), accessible only on password protected and encrypted laptops. Access to this data will only be available to the core research team. Research assistants will sign a confidentiality clause. The detailed War Child Data Management Policy will serve as guidance on all data management and data sharing issues.

All survey data will be collected via Kobo Toolbox. Research Assistants will upload data to the Kobo server at the end of each data collection day. Only the core research team will have access permissions to edit the questionnaires and download the data from the Kobo server. Data will be downloaded from the Kobo server every day and stored as a backup on a secure data server of the R&D Department of War Child. This server is password protected and accessed from password protected and encrypted laptops.

At the end of data collection, the complete data file will be downloaded at the War Child head office from the Kobo server and the master-file will be saved securely on a separate server and uploaded into relevant software for data analysis. All data cleaning and analysis processes will be tracked through saved syntax from data analysis software.

Any hardcopies of data, including informed consent forms, will be stored in a dry, lockable cabinet. Data sets will be accessible by the War Child core research team members. The Research & Development department at War Child has, in all cases, ownership of the research data, except where there is an alternative contractual relationship between War Child and an individual research committee member organisation.

#### **Statistics**

#### Power and sample size

To gain a general appreciation for the required sample size to detect an indirect effect through the primary mediators (Caregiver Distress, Wellbeing, and Harsh Parenting), we used the sample size estimator for joint significance indirect effects developed by Vittinghoff and Neilands (2015). With a two-sided alpha of 0.05, for an intervention-mediator error term correlation coefficient of 0.2, a standard deviation of the mediator of 0.2, and a standard deviation of the random error term of 0.5, a sample of 425 caregivers per group would be sufficient to detect a mean difference of 0.4 (Vittinghoff & Neilands, 2015). All parameter estimates are based on our previous work. Sample size estimators for multiple mediator models are currently unavailable (VanderWeele, 2016); however, O'Rourke and Mackinnon (2015) provide evidence that multiple mediator models have more power than single mediator models. Thus, we expect this study to have sufficient power for multiple mediator models. With a 10% attrition we expect to have 468 families per group with 234 children, totaling 936 caregivers and 468 children. With a total of 40 intervention groups, the final sample size is 960 caregivers (equivalent of 480 families or more) and 400 index children.

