#### **Participants**

Participants will primarily be Dinka-speaking South Sudanese caregivers of children aged 3–14 years, with one index child per family. For families with more than one child in the stated age range, a random index child will be selected among families to be the focus in questionnaires. Thus, when caregivers are completing the parenting and child wellbeing questionnaires, they will do this only for the random index child. Similarly, the random index child will be the one to whom the child-reported questionnaire will be administered. The child-reported questionnaire will be administered to a sub-sample of index children aged 7–14. The total estimated sample size is 960 caregivers (equivalent of 480 families or more) and an estimated 400 index children aged 7–14. We will recruit caregivers from families with two caregivers, as well as from single-caregiver families (see section "Participant Recruitment" below). Thus, our sample of 960 caregivers consisting of: (i) dyads of caregivers for families with two caregivers; and (ii) individual caregivers from single-caregiver households. The total number of families therefore will be at least 480.

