#### **Analyses**

The statistical analyses will be carried out by the trial statistician, who will remain masked to the group randomization until the main analyses are complete. The analyses outlined in this strategy will be primarily based on an intention to treat; a per protocol analysis will be the secondary analysis. The per protocol analysis will include participants who complete the intervention, with completion defined as attending at least seven of the nine sessions, and will exclude any participant who attended fewer than seven sessions. We have powered the study (see the "Sample size" section) as a superiority study at 10 weeks. The first stage of analyses will be a descriptive model of the data to assess completeness of data and the integrity of the data collection system. Participants and area characteristics and demographics will be summarized at baseline. Clinical characteristics that have been measured repeatedly will be summarized at baseline and at the post-randomization follow-up assessments. In addition, patterns of missing data will be described.

The primary outcomes (total score of parenting scale and proxy-reported child psychosocial wellbeing) will be analyzed using linear mixed models to model the mean difference in the total score of parenting scale 10 weeks post-randomization. The linear mixed models will be adjusted for baseline total scores and stratification. A two-level hierarchical model will be employed to improve power and take into account clustering of the parents at the family level. These models utilize maximum likelihood estimation and thus allow for missing outcome data under the missing at random assumption. Associations between post-randomization variables and missingness will be dealt with by multiple imputation, again

under the missing at random assumption. Departures from this assumption will be assessed with a sensitivity analysis. Secondary outcomes, including parental warmth and responsiveness, harsh parenting, caregiver psychosocial wellbeing, stress, and distress, and self-reported child psychosocial wellbeing will be assessed with a similar methodology used for the primary outcomes, using generalized linear mixed models depending on the type of outcome (normal, ordinal).

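### The superiority power claimed for the parenting outcome has no calculation behind it, and the sample-size paragraph it cites states no power, ignores couple clustering, and misstates the attrition step and its unit.

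*Protocol*

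**What the plan says.** The protocol's Power and sample size section contains one calculation. Its aim is "to detect an indirect effect through the primary mediators", and its inputs are introduced by "With a two-sided alpha of 0.05" and "for an intervention-mediator error term correlation coefficient of 0.2", followed by a mediator SD of 0.2 and an error SD of 0.5. It concludes that "a sample of 425 caregivers per group would be sufficient to detect a mean difference of 0.4". No power level is given, and neither the outcome nor the scale of the 0.4 is named. The next step reads "With a 10% attrition we expect to have 468 families per group with 234 children", with totals of 936 caregivers and 468 children. The final size is 960 caregivers, which the Randomization section divides into 480 per arm.

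The Participants section enrols "dyads of caregivers for families with two caregivers" together with single caregivers, and the Randomization section allocates whole families. The Analyses section uses a two-level model to "take into account clustering of the parents at the family level". It also says the study was powered "as a superiority study at 10 weeks", with a cross-reference to the sample-size section. Objective 1 concerns parenting and calls the trial fully powered. The Full structural model section bases the primary mediation analyses on female caregivers only; men and women are combined in the secondary ones.

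**The concern.** Four things do not fit together.

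- The superiority statement cites a calculation that is not in the cited section. This is more than detail left to an analysis plan, because the protocol says the calculation exists and where it is. A reader of a null parenting result could not tell which difference the trial was built to detect.
- Caregivers are counted as if independent, while the design and the model treat the family as the unit. Partners answer about the same index child, so some correlation between their scores is plausible, and it would reduce the information in a between-arm comparison.
- The attrition step multiplies by 1.10 where it should divide by 0.90.
- The result of that step is labelled as families, although its total is in caregivers.

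The reliability of the stated sample size and of the fully powered description is at stake.

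**Working it through.** **Inputs.** From the protocol: two-sided alpha 0.05; 425 caregivers per group; 10% attrition; 480 caregivers per arm; 40 groups per arm of about 12; family randomization. Not in the protocol, so assumed: power (80% and 90% both tried), family ICC (0.1 to 0.5), share of families that are couples, intervention-group ICC and baseline correlation.

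**1. Attrition.** 425 × 1.10 = 467.5, or 468: the protocol's figure. Retaining 425 after 10% loss needs 425/0.90 = 472.2, or 473. Enrolling 468 would leave 468 × 0.90 = 421. The enrolment target is 480, which leaves 480 × 0.90 = 432, so the slip has no consequence by itself.

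**2. Label.** 2 × 468 = 936, the total given for caregivers. If 468 were families per group, every family would have exactly one caregiver, which contradicts the enrolment of couples.

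**3. Can 425 be reproduced?**
- As a plain two-group comparison with difference 0.4 and SD 0.2, 0.5, 0.54 or 1.0, the requirement is 4 to 132 per arm across 80% and 90% power.
- With an assumed formula for the mediator-to-outcome path, N = (z_α + z_β)² × 0.5² / [0.4² × 0.2² × (1 − 0.2²)], the denominator is 0.006144. N is 319 at 80% power and 428 at 90%, in both cases as a **total**.
- So 425 is close to a total for 90% power and was not recovered as a per-group number.

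**4. Couple clustering, taking 425 per group as printed.** For a between-arm comparison the design effect is 1 + ICC × w, where w is the share of caregivers who are in couples. With all couples, w = 1.
- Limit at 10% loss: 432/425 − 1 = 0.0165, so the ICC may be up to about 0.016.
- If 75% or 50% of families are couples, w = 0.857 or 0.667 and the limit is 0.019 or 0.025.
- At 4% loss (the earlier RCT had 96% waitlist completion): 480 × 0.96 = 460.8, and 460.8/425 − 1 = 0.084.

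Effective number per arm is 432/(1 + ICC). Power is Φ[(1.96 + z_power) × √(n_eff/425) − 1.96].

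| Assumed family ICC | Effective n per arm | Power if 425 meant 80% | Power if 425 meant 90% |
|---|---|---|---|
| 0.1 | 393 | 77% | 88% |
| 0.3 | 332 | 70% | 82% |
| 0.5 | 288 | 64% | 76% |

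**5. If 425 is a total.** At ICC 0.5 the effective total is 2 × 288 = 576. Under the path formula, joint power for the two paths is about 96%.

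**6. Female-only mediation.** If every family were a woman and a man, there would be 240 women per arm and 240 × 0.90 = 216 retained (432 in total). That is about half of a per-group requirement of 425. If 425 is a total, 432 covers it, with joint power about 89% under the path formula.

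**7. Parenting difference.** At 80% power with 432 retained per arm, in SD units:

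d = (1.96 + 0.84) × √{(1 − r²) × [(1 + ICC_f) + (1 + ICC_f + 9.8 × ICC_g)] / 432}

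Here r is the baseline correlation, ICC_f the family ICC and ICC_g the intervention-group ICC. The 9.8 is 12 × 0.90 − 1 and applies only to the intervention arm.
- ICC_f 0.2, ICC_g 0, r 0.5: 2.80 × √(0.75 × 2.4/432) = 0.18.
- ICC_f 0.5, ICC_g 0.10, r 0: 2.80 × √(3.98/432) = 0.27.
- No clustering and no baseline: 2.80 × √(2/432) = 0.19.

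**The case against.** The tempting stronger reading is that the trial is underpowered, or that its size holds only if partners' scores are uncorrelated. The documents do not support that, for these reasons:

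- The 0.016 limit needs 425 to be a correct per-group figure. It could not be reproduced as one, and as a total it would leave ample margin.
- The factor 1 + ICC suits a comparison of arm means. For the mediator-to-outcome path, where the mediator differs within a couple, the loss is usually smaller.
- The primary mediation analyses use women only. In a couple of a woman and a man just one partner enters, so couple clustering does not arise there. The open question in that analysis is the number of women.
- Retention may exceed 90%. The protocol reports 99% and 96% waitlist completion in the two earlier studies, though for the control arm only.
- No starting power is stated, so any fall in power is conditional on an assumed one.
- The attrition slip is absorbed by the 480 per arm, and the detectable parenting difference remains modest under clustering.

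All of this stands, and it limits the point to what the protocol states and fails to support. One further defence, that the mixed model deals with clustering, stands only in part: the model puts clustering into the standard errors but does not put it into the planned number. Nor does any of this supply the missing superiority calculation.

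**Conclusion.** The point holds as a fault in the stated power and sample-size reasoning. The superiority claim for the primary objective cites a section that has no such calculation, and that section states no power at all. It also omits the within-family correlation that the analysis model recognizes, gives 468 where 473 is needed, and labels caregivers as families. The last two are errors of text without effect on enrolment.

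The size of the clustering effect is conditional. It rests on 425 per group being the true requirement for independent caregivers, all families being couples, 10% loss, and a between-arm comparison. On those terms the tolerable family ICC is about 0.016, rising to about 0.08 at 4% loss, and power could fall to 64% (from 80%) or 76% (from 90%) at an assumed ICC of 0.5. No ICC is known, so this is a range of possibilities; a shortfall has not been shown. For parenting, the detectable difference of about 0.18 to 0.27 SD suggests power that is undocumented but not evidently poor.

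**What to change.** In Power and sample size:

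- State the power behind 425, and whether 425 is per group or in total.
- If it is per group, replace 468 by 473 and the total 936 by 946; label the counts as caregivers.
- State an assumed family ICC and the expected share of caregivers in couples. Apply 1 + ICC × that share to the between-arm comparison, and give the resulting effective number and power for the fixed 960.
- Restate the mediation power for the expected number of women, since that is the sample of the primary mediation analyses.

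In Analyses, replace the superiority sentence by the parenting difference detectable at 10 weeks with 960 caregivers, naming the assumed family ICC, group ICC and baseline correlation.

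The cost is text and one recalculation. Enrolment and conduct do not change; the printed power may look somewhat less favourable.

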#### **Analyses**

The statistical analyses will be carried out by the trial statistician, who will remain masked to the group randomization until the main analyses are complete. The analyses outlined in this strategy will be primarily based on an intention to treat; a per protocol analysis will be the secondary analysis. The per protocol analysis will include participants who complete the intervention, with completion defined as attending at least seven of the nine sessions, and will exclude any participant who attended fewer than seven sessions. We have powered the study (see the "Sample size" section) as a superiority study at 10 weeks. The first stage of analyses will be a descriptive model of the data to assess completeness of data and the integrity of the data collection system. Participants and area characteristics and demographics will be summarized at baseline. Clinical characteristics that have been measured repeatedly will be summarized at baseline and at the post-randomization follow-up assessments. In addition, patterns of missing data will be described.

The primary outcomes (total score of parenting scale and proxy-reported child psychosocial wellbeing) will be analyzed using linear mixed models to model the mean difference in the total score of parenting scale 10 weeks post-randomization. The linear mixed models will be adjusted for baseline total scores and stratification. A two-level hierarchical model will be employed to improve power and take into account clustering of the parents at the family level. These models utilize maximum likelihood estimation and thus allow for missing outcome data under the missing at random assumption. Associations between post-randomization variables and missingness will be dealt with by multiple imputation, again

under the missing at random assumption. Departures from this assumption will be assessed with a sensitivity analysis. Secondary outcomes, including parental warmth and responsiveness, harsh parenting, caregiver psychosocial wellbeing, stress, and distress, and self-reported child psychosocial wellbeing will be assessed with a similar methodology used for the primary outcomes, using generalized linear mixed models depending on the type of outcome (normal, ordinal).

We will investigate the mediation process of different aspects of caregiver wellbeing and parenting and, through that, examine how these factors affect child wellbeing, helping us understand how best to achieve downstream effects on child wellbeing through psychological interventions. Some of the pathways of interest are illustrated in Figure 4.

[figure not shown]

[figure not shown]
Figure 6 Primary mediation pathways

If the efficacy analysis shows significant between-group differences in the mediators (caregiver stress, caregiver distress, caregiver psychosocial wellbeing, and parenting), then we will use parametric regression models to:

[figure not shown]
- Test for mediation of the intervention on child wellbeing through caregiver stress
- Test for mediation of the intervention on child wellbeing through caregiver distress
- Test for mediation of the intervention on child wellbeing through caregiver psychosocial wellbeing
- Test for mediation of the intervention on child wellbeing through parenting

Since all the measures are continuous, the indirect effects will be calculated by multiplying relevant pathways and bootstrapping will be used to produce valid standard errors for the indirect effects. All analyses will adjust for baseline measures of the mediators (caregiver stress, caregiver distress, caregiver psychosocial wellbeing, and parenting), the outcome (child wellbeing) and putative measured confounders (e.g., socioeconomic status).

Furthermore, these factors will also be analyzed through three sequential mediation models (Figure 5), to assess how the downstream effect of BeThere on child wellbeing is mediated first through (1) caregiver wellbeing, (2) caregiver distress, and (3) caregiver stress, and then through parenting.

Finally, we will also measure the effect of BeThere on caregiver wellbeing, stress, and distress, as mediated through cohesion among the intervention group (Figure 6).

We will assess for the effect of the BeThere intervention on each one of the multiple continuous mediators with the use of linear regression models. We chose an a priori *p*-value of lower than 0.15 to select the appropriate mediators to include in our final mediation analysis (VanderWeele & Vansteelandt, 2014). Multiple mediators require independence with each other. Therefore, we will test independence by examining partial correlations between our mediators after accounting for treatment allocation.

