#### Trial design

#### Design

This study is a two-armed, parallel group randomized controlled trial, with an intent to treat design, a 1:1 allocation ratio, and a waitlist control comparison condition. The study will involve Dinka-speaking primary caregivers of children aged 3–14 and a subsample of their children aged 7–14 in five communities in Bor County, Jonglei State, South Sudan: Pariak, Ghoi, Taragok, Tibek, and Lenguet. Random allocation to intervention and control arms will be done at the family level to ensure caregivers from the same family do not participate in different arms of the study.

We will evaluate the effectiveness of BeThere—a nine-week preventative group psychosocial support intervention for primary caregivers of children aged 3-14-by measuring multiple parenting and psychosocial outcomes among participating caregivers compared to a waitlist control group of caregivers not participating in a parenting intervention. Quantitative data collection will be done by trained research assistants (RAs) using electronic tablets at four timepoints: baseline, midline, endline, and three-month follow up. Prior to the start of data collection, all research instruments will go through a process of translation, adaptation, cognitive interviewing, and pilot testing. The primary outcome of the study will be an overall score on parenting. Secondary outcomes will be child wellbeing (caregiver- and childreported), caregiver stress, distress, and wellbeing, as well as harsh parenting and parental warmth and responsiveness. Additionally, demographics data will be collected from caregivers and children. We will also record participant attendance to intervention sessions, along with facilitator competence to deliver the intervention and their fidelity in delivering the intervention as planned. Additional qualitative data will be gathered via focus group discussions and key informant interviews. The study will be conducted between January and July 2025.

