#### **Exclusion** criteria

- Under 18 years of age
- Participation by either caregiver in a parenting or stress management intervention in the past six months
- Family does not have a child aged 3–14 years

- Anyone who is unable, even with assistance, to complete the assessment questionnaires
- Unwillingness of either caregiver to give informed consent
- Not fluent in Dinka

Based on the successful implementation of the design in the pilot RCT and RCT in Lebanon, a waitlist control will serve as the comparison group in this study. Participants in the waitlist control group will be given the opportunity to participate in the intervention after the 3-month follow-up assessment has been completed.

This study will involve a waitlist control group for two key reasons:

- 1) While the risk of a nocebo effect among research participants randomized into the control group in waitlist-controlled psychological treatment trials has been raised (Furukawa et al., 2014; Gold et al., 2017; Steinert et al., 2017), there is currently little evidence to show that this is the case for preventative interventions (Gold et al., 2017; Miller, et al., 2023).
- 2) The BeThere intervention has already been shown to be effective among caregivers in Lebanon. Considering the vulnerability of the target population and the lack of existing mental health and psychosocial support services, we do not want to deny control group participants access to the intervention.

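### The secondary per-protocol rule is not limited to the BeThere arm: read literally it keeps no controls, and read as intended it is a comparison that randomisation does not protect

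*Protocol*

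**What the plan says.** The Protocol's Analyses section bases the analysis mainly on intention to treat and adds that "a per protocol analysis will be the secondary analysis". It defines the set in two clauses. The first reads: "The per protocol analysis will include participants who complete the intervention, with completion defined as attending at least seven of the nine sessions". The second says that the analysis "will exclude any participant who attended fewer than seven sessions". Neither clause names an arm, and the control arm gets no per-protocol definition.

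The text under Exclusion criteria says when controls can attend: "Participants in the waitlist control group will be given the opportunity to participate in the intervention after the 3-month follow-up assessment has been completed". The Attendance section records attendance at BeThere sessions only.

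The outcome models are linear mixed models "to model the mean difference in the total score of parenting scale 10 weeks post-randomization", adjusted for the baseline total score and stratification. The section names no method for dealing with selection on attendance.

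**The concern.** The rule has two readings, and neither gives a sound between-arm estimate. Taken word for word, it removes the comparator. Taken as surely meant, it sets the BeThere caregivers who came to seven or more sessions against every control, including those who would have stopped attending had they been allocated to BeThere.

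Attendance is unlikely to be unrelated to outcome. Under the criteria for discontinuing the intervention, a repeatedly disruptive participant may be asked to leave the sessions while staying in the study. If that happens before the seventh session, the person leaves the BeThere per-protocol set, while the same kind of person stays in the control set. The Randomization section also credits proximity with raising attendance.

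At stake is how the named secondary analysis is read. The background section describes an earlier trial in which many participants could not receive the whole programme. A per-protocol estimate may therefore be taken as the effect of full attendance, which it would not validly estimate.

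**Working it through.** **1. Starting population.** The Randomization section gives 5 communities with 96 caregivers per arm each: 5 × 96 = 480 per arm, 960 in total. The group count agrees: 5 × 8 groups × 12 = 480.

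**2. Literal rule.** Let p be the share of the BeThere arm attending at least seven sessions; the protocol gives no value.

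- BeThere: 480p kept (288 at p = 0.6; 384 at p = 0.8).
- Waitlist: sessions attended by 10 weeks and by the 3-month follow-up = 0, which is fewer than 7, so 0 of 480 are kept.

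No between-arm contrast can be estimated.

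**3. Intended rule.** 480p attenders against all 480 controls. Let d be the difference between completers and non-completers in the outcome they would have had untreated, after the planned adjustment. Then

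bias = completer mean − whole-arm mean = m_c − [p·m_c + (1 − p)·m_n] = (1 − p)·d.

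Both p and d are assumptions. In SD units:

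| p | d = 0.2 | d = 0.3 | d = 0.5 |
|---|---|---|---|
| 0.6 | 0.08 | 0.12 | 0.20 |
| 0.7 | 0.06 | 0.09 | 0.15 |
| 0.8 | 0.04 | 0.06 | 0.10 |
| 0.9 | 0.02 | 0.03 | 0.05 |

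If d is negative, the same sizes apply against BeThere.

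**4. Yardstick.** With the protocol's 10% attrition, 480 × 0.9 = 432 per arm remain. At p = 0.7 the contrast is about 302 against 432. The difference detectable with 80% power, ignoring clustering, is 2.80 × √(1/302 + 1/432) = 0.21 SD. The 0.09 SD in the table is a little under half of that.

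**5. Second model, no true effect.** Let r be the correlation between propensity to attend and the adjusted outcome (assumed). With c = Φ⁻¹(1 − p), bias = r·φ(c)/p and SE = √(1/(480p) + 1/480), ignoring attrition and clustering. For p = 0.6 to 0.9 and r = 0.1 to 0.3:

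- The spurious difference is 0.02 to 0.19 SD.
- A two-sided 5% test rejects in about 6% to 74% of trials.
- At p = 0.8 and r = 0.2: 0.07 SD and about 18%.
- At r = 0: no bias and 5%.

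The two models give nearly the same range, but both rest on assumed inputs.

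**The case against.** The strongest reply is that completing the intervention has meaning only for caregivers allocated to it, so nobody would actually drop the waitlist arm. That is right about intent: a reader might infer that the analysis cannot be run, but a few added words cure that. They do not cure the second reading. Nor is this merely detail left to a statistical analysis plan, because the protocol itself fixes the rule.

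It can also be said that every per-protocol analysis has this weakness, that intention to treat is correctly primary, and that no stated objective asks for a dose effect. All of that stands and limits the severity. Several design features also work against selective attendance: a commitment before randomisation to attend all nine sessions, nearby venues, on-site childcare, and session times chosen around paid work. They reduce selection but cannot identify which controls would have attended. Baseline adjustment removes part of what is left; how much cannot be known from the protocol.

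Two stronger readings are tempting but unsupported. One is that the bias favours BeThere. Nothing in the protocol says that attenders are less distressed, and more distressed caregivers might attend more. The other is that the earlier trial's dose comparison is flawed in the same way. The background section attributes the reduced dosage there to lockdowns, economic crisis and unrest, and does not describe how that comparison was analysed.

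**Conclusion.** The point holds as a should-fix, not a must-fix. The stated per-protocol rule either leaves 0 of 480 controls or, as evidently meant, compares selected BeThere attenders with an unselected control arm. The first follows directly from the protocol's text and needs no assumption. The second is a matter of design: randomisation does not protect the contrast, whatever the bias turns out to be.

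The 0.02 to 0.20 SD range illustrates what assumed completion of 60% to 90% and an assumed residual difference of 0.2 to 0.5 SD would produce; it is not an estimate for this trial. The primary intention-to-treat analysis does not depend on this rule.

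**What to change.** Change the per-protocol text in three ways:

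1. Apply the attendance criterion to the BeThere arm only, and state that all controls are retained.
2. Label that contrast exploratory and non-randomised.
3. Make the secondary adherence analysis a complier-average causal effect in all randomised caregivers. Use allocation as the instrument for sessions attended (0 to 9, set to 0 in the waitlist arm), adjust for baseline score and community, and use standard errors that account for clustering by family and by group. Because groups are single-sex, two caregivers of different sex from one family sit in different groups, so the two levels are crossed.

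The cost is wording and analysis time; attendance registers are already planned. State the downsides:

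- **Precision.** The interval will be wider.
- **Exclusion restriction.** Allocation must act only through a caregiver's own attendance. This needs discussion, since both caregivers of a family share an arm and the contamination section allows sharing content within the household.
- **Linear dose.** Equal benefit per session is doubtful for a parenting outcome when sessions 1 to 4 address caregiver wellbeing and 5 to 8 address parenting.

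If a binary version with the seven-session cut is also shown, note that it codes attenders of one to six sessions as untreated. At an assumed 70% completion it divides the intention-to-treat difference by 0.7 (a factor of 1.43) and credits completers with all of it. If partial attendance also helps, that overstates the effect.
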